2.2 Background

Primary surgical resection remains the first-line treatment for small HCC (<3 cm) in patients with preserved liver function. Child-Pugh class A patients with small HCC have shown a 5-year overall survival rate around 70% following surgical resection. Unfortunately, many patients are not eligible for surgical resection either secondary to tumor location, underlying portal hypertension or co-morbidities. The NCCN guidelines recommend surgical resection when possible, with locoregional therapy being recommended for patients who are not candidates for resection (recommending ablation, arterial directed therapies, and external beam radiation therapy as category 2B recommendations).

There are no data directly comparing stereotactic body radiotherapy (SBRT) to high-dose segmental radioembolization (radiation segmentectomy). Both of these treatment approaches have relatively small published data sets demonstrating efficacy and relative safety, but a head-to-head comparison has yet to be performed. In addition to efficacy and toxicity, patient-reported outcomes (PROs) such as quality of life (QoL) and patient out-of-pocket cost of care should play a role in the choice of treatment of these patients. The majority of patients with HCC have chronic liver disease which may already affect their QoL. Many patients, particularly at our institution, also travel multiple hours for their treatments and the difference between the number of visits required for radioembolization and SBRT may affect their treatment choice and PROs.

2.3 Risk/Benefit Assessment

There is very minimal risk outside the standard of care as both treatment options are currently utilized and have category 2B recommendations from the NCCN. Expected toxicities of both treatment arms include fatigue and potential worsening of liver function.

The only added non-standard of care risk would be for RS patents surrounding their functional HIDA scan. The risks involved in a HIDA scan are minimal. They include the following:

- 1. Radiation exposure; a very small amount of radioactive material is used and the radiation exposure is well below the level that causes adverse effects.
- 2. Allergic reactions to the radioactive material; however, this is extremely rare, without documented cases.
- 3. Discomfort, bruising or rash at the injection site or discomfort while lying on the table for the required amount of time for the scan.

3.0 STUDY DESIGN

The proposed study is a single site, prospective, randomized pilot study to assess the feasibility of recruitment of patients into a trial evaluating the efficacy and tolerability of selective transarterial Y90 radioembolization (radiation segmentectomy) versus stereotactic body radiation therapy (SBRT) for solitary early stage (≤ 3cm) hepatocellular carcinoma (HCC).

4.0 STUDY OBJECTIVES AND ENDPOINTS

4.1 Primary Objective

To assess feasibility as measured by screen failures and rate of recruitment into a randomized trial comparing RS and SBRT

Primary Endpoint: Recruitment rates measured at 6 and 12 months and screen failures assessed by the screen failure form at the time patients are approached for enrollment to ascertain specific reasons why patients may choose not to enroll

4.2 Secondary Objectives (SO)/ Secondary Endpoints (SE)

- SO: To compare the proportion of patients with toxicities (≥ grade 4) using CTCAE version 5.0 between RS and SBRT for patients with small (≤3 cm) solitary hepatocellular carcinoma (HCC). Only those toxicities at least possibly related to treatment will be considered.
 - **SE:** Laboratory (CBC, CMP, INR)/clinical toxicities measured using CTCAE version 5.0 up to 6 months post treatment.
- 2. **SO**: To compare the mean change in hepatobiliary function, as measured 3 months after treatment using a functional HIDA scan, between RS and SBRT for patients with small (≤3 cm) solitary hepatocellular carcinoma (HCC). SE: Change in % radiotracer extraction from baseline, on functional HIDA scan, 3 months after treatment
- 3. **SO:** To compare the mean change in patient-reported outcomes (PROs) from baseline, at 1, 3 and 6 months, between RS and SBRT, for patients with small (≤3 cm) solitary hepatocellular carcinoma (HCC), using FACT -G and COST FACIT questionnaires. **SE:** Change in FACT-G and COST FACIT from baseline at 1, 3 and 6 months
- 4. SO: To compare the disease-free survival (DFS) rates of RS and SBRT at 2 years using mRECIST on CT or MR for patients with small (≤3 cm) solitary hepatocellular carcinoma (HCC).SE: DFS at 2 years after treatment completion as measured with mRECIST on CT or MR
- 5. **SO:** To compare time-to-secondary treatment (TTST) between RS and SBRT for patients with small (≤3 cm) solitary hepatocellular carcinoma (HCC) up to 2 years after initial treatment. SE: TTST for target tumor up to 2 years following treatment.

6. **SO:** To measure the objective response rate (ORR) of radiation segmentectomy (RS) and stereotactic body radiation therapy (SBRT) as measured at 6 months using mRECIST (appendix IV) for patients with small (≤3 cm) solitary hepatocellular carcinoma (HCC) to better allow for an appropriately powered trial evaluating the efficacy of these treatments. **SE:** ORR at 6 months after completion of treatment using mRECIST on multiphase CT or MR.

Table 1: Justification for Endpoints

	OBJECTIVES	ENDPOINTS	JUSTIFCATION FOR ENDPOINTS		
Pri	mary				
1.	To assess feasibility as measured by screen failures and rate of recruitment into a randomized trial comparing RS and SBRT	 a. Recruitment rates measured at 6 and 12 months b. Screen failure form 	 a. Given the technical differences between the two modalities, recruitment may prove difficult so analyzing recruitment rates at 6 and 12 months may reveal futility. b. Screen failure form will help PI assess feasibility for a larger scale study. 		
Sec	ondary				
1.	To compare the proportion of toxicities (≥ grade 4) using CTCAE between RS and SBRT for patients with small (≤3 cm) solitary hepatocellular carcinoma (HCC).	Laboratory (CBC, CMP, INR)/clinical toxicities measured using CTCAE	Provide a measure of each treatment's potentially deleterious effect on the surrounding liver parenchyma.		
2.	To compare the change in hepatobiliary function, as measured 3 months after treatment using a functional HIDA scan, between RS and SBRT for patients with small (≤3 cm) solitary hepatocellular carcinoma (HCC).	Change in % radiotracer extraction from baseline, on functional HIDA scan, 3 months after treatment	Provide a measure of each treatment's potentially deleterious effect on the surrounding liver parenchyma.		
3.	To compare the change in patients reported outcomes from baseline, at 1, 3 and 6 months, between RS and SBRT, for patients with small (≤3 cm) solitary hepatocellular carcinoma (HCC), using FACT-G and COST FACIT.	Change in FACT-G and COST FACIT from baseline at 1, 3 and 6 months	Provide insight into whether or not one treatment is more deleterious to a patient's quality of life overall, as measured by the patient themselves.		

4.	To compare the disease- free survival (DFS) rates of RS and SBRT at 2 years using mRECIST on CT or MR for patients with small (≤3 cm)	DFS at 2 years after treatment completion as measured with mRECIST on CT or MR	DFS at 2 years will allow for assessment of both target and non-target recurrence in this population who are often prone to have new tumors secondary to cirrhosis.
5.	To compare time-to- secondary treatment (TTST) between RS and SBRT for patients with small (≤3 cm) solitary hepatocellular carcinoma (HCC) up to 2 years after initial treatment.	TTST for target tumor up to 2 years following treatment.	TTST will allow for some measure of the long term efficacy of the treatment as these tumors are often treated multiple times.
6.	To measure the objective response rate (ORR) of radiation segmentectomy (RS) and stereotactic body radiation therapy (SBRT) as measured at 6 months using mRECIST for patients with small (≤3 cm) solitary hepatocellular carcinoma (HCC).	ORR at 6 months after completion of treatment using mRECIST on multiphase CT or MR.	ORR is a common endpoint for the measure of efficacy of liver directed therapy. This may also help provide an estimate which will be used for the sample size calculation for the following large scale study

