8.2 Safety and Other Assessments

Both treatment arms are currently being performed as standard of care. The PI will ultimately monitor safety with direct monitoring for AEs collected by research personnel with discussion with the PI as needed. Comparison of toxicities (≥ grade 4) will be performed as a secondary endpoint. The most common expected toxicities are fatigue and liver toxicity.

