10.3 Sample Size Projections

The primary objective of the pilot study will be to access feasibility. 20 patients in total will be enrolled, with up to 10 patients per arm (depending on the amount of screen fails). These numbers should be sufficient for the assessment of feasibility.

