13.3 Time Period and Frequency for Event Assessment and Follow-Up

The occurrence of an adverse event (AE) or serious adverse event (SAE) may come to the attention of study personnel during study visits and interviews of a study participant presenting for medical care or upon review of the medical record.

Adverse events will be recorded with start dates occurring any time after informed consent is obtained until 7 (for non-serious AEs) or up to 30 days (for SAEs) after the 6 month visit. At each study visit, the investigator will inquire about the occurrence of AE/SAEs since the last visit. Events will be followed for outcome information until adequate resolution or stabilization.

All AEs including local and systemic reactions not meeting the criteria for SAEs will be captured on the appropriate case report form (CRF). Information to be collected includes event description, time of onset, clinician's assessment of severity, relationship to study product (assessed only by those with the training and authority to make a diagnosis), and time of resolution/stabilization of the event. All AEs occurring while on study must be documented appropriately regardless of relationship. All AEs will be followed to adequate resolution.

Any medical condition that is present at the time that the participant is screened will be considered as baseline and not reported as an AE. However, if the study participant's condition deteriorates at any time during the study, it will be recorded as an AE.

Changes in the severity of an AE will be documented to allow an assessment of the duration of the event at each level of severity to be performed. AEs characterized as intermittent require documentation of onset and duration of each episode.

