14.1 Data and Safety Monitoring Committee

The IUSCC Data and Safety Monitoring Committee (DSMC) is responsible for oversight of subject safety, regulatory compliance, and data integrity for this trial. The DSMC will review this study annually to review overall trial progress, toxicity, compliance, data integrity, and accrual per the Institutional DSMP.

Furthermore, the DSMC conducts an administrative review of serious adverse events (SAEs), deviations, reportable events, and any other outstanding business. Major issues may require further DSMC review or action.

For any increase in frequency of grade 3 or above adverse events (above the rate reported in the Investigator Brochure or package insert), the principal investigator will notify the DSMC Chair immediately. The notification will include the incidence of study adverse events, grades, and attributions, as well as investigator statements regarding comparison with risks per the IB/ package insert.

At any time during the conduct of the trial, if it is the opinion of the investigators that the risks (or benefits) to the subject warrant early closure of the study, the DSMC Chair and Compliance Officer must be notified within 1 business day via email, and the IRB must be notified within 5 business days. Alternatively, the DSMC may initiate suspension or early closure of the study based on its review.

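### The between-arm toxicity comparison counts only related grade 4 or higher events, so it misses liver and clinical harm below grade 4 that the trial already records

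*Combined protocol and SAP*

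**What the plan says.** Section 4.2 item 1 gives the objective as "To compare the proportion of patients with toxicities (≥ grade 4) using CTCAE version 5.0 between RS and SBRT" and adds: "Only those toxicities at least possibly related to treatment will be considered". The endpoint line beneath it names no grade; it refers to "clinical toxicities measured using CTCAE version 5.0 up to 6 months post treatment". The grade 4 cut-off sits in the objective and is repeated in the synopsis, Table 1, section 8.2, the hypotheses of 10.2.2 item 1 and the analysis in 10.5.3 item 1. That analysis is a proportion per arm with a 95% confidence interval and Fisher's exact test.

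Table 1 states the purpose: "Provide a measure of each treatment's potentially deleterious effect on the surrounding liver parenchyma". Section 8.2 adds: "The most common expected toxicities are fatigue and liver toxicity".

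Collection is wider than the comparison. Section 13.1.1 grades adverse events by CTCAE version 5.0. Section 13.3 has all of them documented with no grade floor, and says "Changes in the severity of an AE will be documented to allow an assessment of the duration of the event at each level of severity". Blood count, metabolic profile and INR are drawn at 1, 3 and 6 months (sections 1.3 and 8.1). Section 10.5.4 adds no analysis by grade.

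**The concern.** The purpose is to show what each treatment does to the surrounding liver, and the toxicities the protocol expects are fatigue and liver toxicity. With the cut-off at grade 4, a patient with a related grade 3 bilirubin or INR abnormality is scored the same as a patient with none. The lower grades will be in the database, but nothing commits the investigators to analyse them, and a table added after the data are seen carries less weight than one planned beforehand.

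Section 3.0 says the trial being prepared would evaluate efficacy and tolerability. If severe events are rare, the pilot could report few or none in either arm. It would then pass on little about tolerability, and a reader could take the result as evidence that the two treatments are equally safe.

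**Working it through.** **Inputs**

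- Up to 10 patients per arm, 20 in total (section 10.3). If the 10% unanalyzable accruals of section 9.0 were not replaced, 9 per arm.
- Fisher's exact test and 95% confidence intervals (10.5.3 item 1). Two-sided, because the alternative in 10.2.2 is inequality.
- Alpha is not stated; 0.05 is assumed.
- No toxicity rate is stated for any grade. Every rate below is an assumption.

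The plan has no power or toxicity figure to reproduce. Its only arithmetic, 2 × 10 = 20, is consistent.

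**Step 1: how many patients would be counted.** With the same rate p in both arms, the expected number of affected patients is 20p and the chance of none is (1 − p)^20, or (1 − p)^18 with 9 per arm.

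| Assumed rate | Expected among 20 | Chance of none, 20 patients | Chance of none, 18 patients |
|---|---|---|---|
| 1% | 0.2 | 82% | 83% |
| 2% | 0.4 | 67% | 70% |
| 5% | 1.0 | 36% | 40% |
| 10% | 2.0 | 12% | 15% |
| 20% | 4.0 | 1% | 2% |

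No events at all is more likely than not only when (1 − p)^20 > 0.5, that is p < 1 − 0.5^(1/20) = 3.4%.

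**Step 2: what a zero would mean.** The exact 95% upper limit for 0/10 is 1 − 0.025^(1/10) = 30.8%. For 0/9 it is 33.6%.

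**Step 3: what Fisher's test needs.** Against 0/10, the two-sided p for x/10 is 2 × C(10,x)/C(20,x):

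- x = 4: 2 × 210/4845 = 0.087
- x = 5: 2 × 252/15504 = 0.033

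Half of one arm must be affected when the other has no events. Steps 2 and 3 depend on the arm size and not on the grade chosen.

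**Step 4: what a lower threshold would gain.** Suppose the grade 3 or higher rate were 10-20%. From the table, 2-4 affected patients would be expected, with a 12-1% chance of none, so there would usually be something to describe. It would not give a powered test. Full enumeration of the Fisher test at 10 per arm gives 5.7% power for 10% versus 30%, and 13.2% for 20% versus 50%. The normal approximation needs 62 and 39 per arm respectively for 80% power. The estimates would also be imprecise: 1/10 has an exact 95% interval of 0.3% to 44.5%.

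**The case against.** The strongest reply is that grade 4 or higher is a deliberate severe-harm endpoint placed beside more sensitive measures. Table 1 gives the HIDA endpoint the same justification sentence, and that endpoint is continuous and does not depend on event counts. Fatigue is partly covered by FACT-G, which has an item on lack of energy and is compared between arms. The endpoint line in 4.2 has no grade floor, so nothing forbids a summary by grade. The primary aim is recruitment, and the pilot estimate named for sample-size planning is ORR.

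Much of this stands, and it rules out four stronger readings that a reader might infer:

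- *That the result will probably be 0/10 versus 0/10.* The documents give no rate. At 5%, at least one event is more likely than not (64%). Section 5.1 also admits Child-Pugh scores up to 7 and bilirubin to just under 4.0 mg/dL, so a very low rate cannot be taken for granted.
- *That the trial cannot measure liver harm.* Grade 4 or higher captures severe harm, and HIDA measures liver function.
- *That section 14.1 contradicts the endpoint.* Its trigger, "For any increase in frequency of grade 3 or above adverse events", concerns rates above those in the Investigator Brochure or package insert. An oversight alarm and a between-arm comparison may use different grades.
- *That the grade cut-off causes the weak test.* Steps 2 and 3 show that this comes from 10 per arm.

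What the reply does not answer is that HIDA is a single functional measure at 3 months. It does not record clinical or laboratory toxicity, or anything arising between 3 and 6 months. A summary by grade is permitted, but it is not planned.

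**Conclusion.** The point holds as a matter of sensitivity. The comparison ignores all harm below grade 4, although its stated purpose is to show harm to the liver and the lower grades are already collected. This follows from the text and needs no assumed rate.

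The size does rest on assumption. A grade 4+ rate of 1-5% means 0.2-1.0 affected patients expected among 20 and an 82-36% chance of none. At 10% the chance of none falls to 12%, and at 20% to 1%.

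The consequence is moderate: this is a secondary endpoint in a feasibility pilot, and HIDA covers part of the same ground. Lowering the threshold improves description and does not rescue the test. At any threshold the arms are too small for a non-significant result to be read as equal toxicity.

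A related inconsistency needs reconciling. The attribution rule of 4.2 is absent from 10.2.2 and 10.5.3, which speak of any toxicities. As written, the objective and the analysis could count different events.

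**What to change.** - In 10.5.3 item 1, report by arm the proportion of patients with a grade 3 or higher toxicity with exact 95% confidence intervals, and keep grade 4 or higher as a reported subset.
- Make the same change in the synopsis, 4.2 item 1, Table 1, 8.2 and 10.2.2 item 1. Editing only some of these would leave the protocol contradicting itself.
- Prespecify one table of worst grade per patient by arm for bilirubin, INR, albumin, platelets and fatigue. State how baseline abnormality is handled, since 5.1 admits raised bilirubin and low albumin. State also whether the weekly on-treatment labs of the SBRT arm (7.1.2) count, since 7.1.1 describes no weekly counterpart for RS.
- Apply the at-least-possibly-related rule of 4.2 in every statement of this endpoint.
- State that the toxicity comparison is descriptive, and that a null result will be reported with its interval and not as evidence of equal toxicity.

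The cost is wording in six places and one extra table, with no new visits or tests. The downside is that the reported toxicity proportions will be higher than under grade 4 or higher alone.

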1.0 PROTOCOL SUMMARY

1.1 Synopsis

TITLE:	Yttrium-90 Radiation Segmentectomy versus Stereotactic Body Radiation Therapy (SBRT) for the Treatment of Early Stage Hepatocellular Carcinoma (HCC): A Pilot Study
STUDY DESCRIPTION:	The proposed study is a single site, prospective, randomized pilot study to assess the feasibility of recruitment of patients into a trial evaluating the efficacy and tolerability of selective transarterial Y90 radioembolization (radiation segmentectomy) versus stereotactic body radiation therapy (SBRT) for solitary early stage (≤ 3cm) hepatocellular carcinoma (HCC).
OBJECTIVES:	Primary Objective: 1. To assess feasibility as measured by screen failures and rate of recruitment into a randomized trial comparing RS and SBRT Secondary Objectives: 1. To evaluate the proportion of patients with any toxicities (≥ grade 4) using CTCAE between RS and SBRT for patients with small (≤3 cm) solitary hepatocellular carcinoma (HCC). 2. To evaluate the mean change in hepatobiliary function, as measured 3 months after treatment using a functional HIDA scan, between RS and SBRT for patients with small (≤3 cm) solitary hepatocellular carcinoma (HCC). 3. To evaluate the mean change in patient-reported outcomes from baseline, at 1, 3 and 6 months, between RS and SBRT, for patients with small (≤3 cm) solitary hepatocellular carcinoma (HCC), using the Functional Assessment of Cancer Therapy- General (FACT-G) and COST FACIT questionnaires. 4. To evaluate the disease-free survival (DFS) rates of RS and SBRT at 2 years using mRECIST on CT or MR for patients with small (≤3 cm) solitary hepatocellular carcinoma (HCC). 5. To evaluate time-to-secondary treatment (TTST) between RS and SBRT for patients with small (≤3 cm) solitary hepatocellular carcinoma (HCC) up to 2 years after initial treatment. 6. To measure the objective response rate (ORR) of radiation segmentectomy (RS) and stereotactic body radiation therapy (SBRT) as measured at 6 months using mRECIST (appendix IV) for patients with small (≤3 cm) solitary hepatocellular carcinoma (HCC) to better allow for an appropriately powered trial evaluating the efficacy of these treatments

[figure not shown]
Protocol Version: 15DEC2021

5

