10.2.2 Secondary Objectives/Endpoints

1. SE: Laboratory (CBC, CMP, INR)/clinical toxicities measured using CTCAE version 5.0

SO: To compare the proportion of any toxicities (\geq grade 4) using CTCAE version 5.0 between RS and SBRT for patients with small (\leq 3 cm) solitary hepatocellular carcinoma (HCC) up to 6 months after treatment.

NH: The proportion of any toxicities (\geq grade 4), using CTCAE version 5.0, between RS and SBRT for patients with small (\leq 3 cm) solitary hepatocellular carcinoma (HCC) are equal.

AH: The proportion of any toxicities (\geq grade 4), using CTCAE version 5.0, between RS and SBRT for patients with small (\leq 3 cm) solitary hepatocellular carcinoma (HCC) are not equal.

2. **SE:** Change in % radiotracer extraction from baseline, on functional HIDA scan, 3 months after treatment

SO: To compare the mean change in hepatobiliary function, as measured 3 months after treatment using a functional HIDA scan, between RS and SBRT for patients with small (≤3 cm) solitary hepatocellular carcinoma (HCC).

NH: The mean change in hepatobiliary function, as measured 3 months after treatment using a functional HIDA scan, will be equal between RS and SBRT for patients with small (≤3 cm) solitary hepatocellular carcinoma (HCC).

AH: The mean change in hepatobiliary function, as measured 3 months after treatment using a functional HIDA scan, will not be equal between RS and SBRT for patients with small (≤3 cm) solitary hepatocellular carcinoma (HCC).

3. **SE:** Change in FACT-G and COST FACIT from baseline at 3 and 6 months

SO: To compare the mean change in patient-reported outcomes from baseline, at 3 and 6 months, between RS and SBRT, for patients with small (≤3 cm) solitary hepatocellular carcinoma (HCC), using FACT-G and COST FACIT.

NH: The mean change in patient-reported outcomes from baseline, at 1, 3 and 6 months, will be equal between RS and SBRT, for patients with small (≤3 cm) solitary hepatocellular carcinoma (HCC), using FACT-G and COST FACIT.

AH: The mean change in patient-reported outcomes from baseline, at 1, 3 and 6 months, will not be equal between RS and SBRT, for patients with small (≤3 cm) solitary hepatocellular carcinoma (HCC), using FACT-G and COST FACIT.

4. SE: DFS at 2 years after treatment completion as measured with mRECIST on CT or MR

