10.5.3 Analysis of the Secondary Endpoint(s)

The secondary research questions to be addressed are as follows:

- 1. To compare the proportion of any toxicities (≥ grade 4) using CTCAE between RS and SBRT for patients with small (≤3 cm) solitary hepatocellular carcinoma (HCC).
 - The proportion of patients with toxicities will be provided along with corresponding 95% confidence intervals. Toxicity rates will be compared using a Fisher's Exact Test.
- 2. To compare the mean change in hepatobiliary function, as measured 3 months after treatment using a functional HIDA scan, between RS and SBRT for patients with small (≤3 cm) solitary hepatocellular carcinoma (HCC).
 - A two-sample t-test will be used to analyze mean changes in liver function as measured by functional HIDA scan.
- 3. To compare the mean change in patient-reported outcomes from baseline, at 3 and 6 months, between RS and SBRT, for patients with small (≤3 cm) solitary hepatocellular carcinoma (HCC), using FACT-G and COST FACIT.
 - A two-sample t-test will be used to analyze mean changes in patient reported outcomes as measured using FACT-G and COST FACIT.
- 4. To compare the disease-free survival (DFS) rates of RS and SBRT at 2 years using mRECIST on CT or MR for patients with small (≤3 cm) solitary hepatocellular carcinoma (HCC).
 - DFS rates will be compared using Kaplan-Meier estimates with a log rank analysis.
- 5. To compare time-to-secondary treatment (TTST) between RS and SBRT for patients with small (≤3 cm) solitary hepatocellular carcinoma (HCC) up to 2 years after initial treatment.
 - TTST rates will be compared using Kaplan-Meier estimates with a log rank analysis.

6. The proportion of patients with ORR at 6 months will be provided along with corresponding 95% confidence intervals. ORR rates will be compared using a Fisher's Exact Test.

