13.1.1 Adverse Event (AE)

An adverse event is defined as an untoward medical occurrence associated with the use of an intervention in humans, whether or not considered intervention related. An adverse event can be ANY unfavorable and unintended sign (e.g., an abnormal laboratory finding), symptom, or disease temporarily associated with the use of an intervention, whether or not considered related to the intervention (attribution of 'unrelated', 'unlikely', 'possible', 'probable', or 'definite'). Adverse events will be graded according to CTCAE version 5.0

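### Section 13.3 stops recording non-serious adverse events 7 days after the 6-month visit while 13.4 and footnote H say 30 days for all; section 10 also omits the relatedness rule for the grade 4 or higher toxicity endpoint

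*Combined protocol and SAP*

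**What the plan says.** **Recording period.** Section 13.3 records adverse events from consent until 7 days after the 6-month visit if non-serious, and up to 30 days after it if serious. Section 13.4 and footnote H of the Schedule of Events (1.3) both give 30 days after that visit and do not separate serious from non-serious events. The schedule places the visit 180 days from the end of treatment, plus or minus 30 days. The toxicity endpoint in 4.2 runs up to 6 months after treatment and includes laboratory toxicities.

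**Which events count.** Item 1 of section 4.2 sets the rule: "Only those toxicities at least possibly related to treatment will be considered". It appears nowhere else.
- Synopsis (1.1): "To evaluate the proportion of patients with any toxicities (≥ grade 4) using CTCAE between RS and SBRT".
- Table 1: "To compare the proportion of toxicities (≥ grade 4) using CTCAE between RS and SBRT".
- Section 8.2: "Comparison of toxicities (≥ grade 4) will be performed as a secondary endpoint".
- Section 10.2.2, null hypothesis: "NH: The proportion of any toxicities".
- Section 10.5.3, research question: "To compare the proportion of any toxicities (≥ grade 4) using CTCAE between RS and SBRT".

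The analysis line in 10.5.3 is per patient: "The proportion of patients with toxicities will be provided along with corresponding 95% confidence intervals". It assigns Fisher's exact test to the comparison.

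**The concern.** Site staff following 13.3 would stop recording non-serious events 23 days sooner than staff following 13.4. The plan does not say which section governs. Footnote H refers to a section 12.4, but section 12 ends at 12.3, so the cross-reference does not settle the matter. If recording stops before the toxicity window closes, a qualifying non-serious event could go unrecorded.

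The second issue is in the analysis. Someone programming the toxicity comparison from section 10 alone has no instruction to filter on attribution and could test an all-cause numerator. The choice can change the result because attribution is assigned by the clinical investigator (13.1.3) in a trial where overall blinding is not feasible (7.2). The only blinded assessors described are the radiologists who read response and disease-free survival.

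**Working it through.** The plan gives no power, significance level or expected rate for this endpoint, so it has no figure to reproduce. The check is day arithmetic, a comparison of wording, and a sense of scale.

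**1. Recording period.** Let v be the day of the 6-month visit, counted from the end of treatment. From the schedule, v runs from 180 − 30 = 150 to 180 + 30 = 210, which is 61 permitted days. Assume the toxicity window closes on day 180.
- Under 13.3, non-serious recording ends on day v + 7. The shortfall is 180 − (v + 7) = 173 − v when positive.
- Under 13.4 and footnote H, recording ends on day v + 30. The shortfall is 180 − (v + 30) = 150 − v, which is never positive.

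| Visit day | 13.3 ends (non-serious) | Shortfall | 13.4 and footnote H end | Shortfall |
|---|---|---|---|---|
| 150 | 157 | 23 | 180 | 0 |
| 172 | 179 | 1 | 202 | 0 |
| 173 | 180 | 0 | 203 | 0 |
| 180 | 187 | 0 | 210 | 0 |
| 210 | 217 | 0 | 240 | 0 |

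Under 13.3 a shortfall arises for visits on days 150 to 172, which is 23 of the 61 permitted days.

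Sensitivity to the meaning of 6 months:
- If it means 183 days, the largest shortfalls are 183 − 157 = 26 days under the 7-day rule and 183 − 180 = 3 days under the 30-day rule.
- If it means through the 6-month visit, the shortfall is zero under both.

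**2. Which events could fall in the gap.** Only non-serious ones, because all three places allow 30 days for serious events. Section 13.1.2 defines seriousness by outcome or medical importance, not by CTCAE grade, so a grade 4 laboratory value can be non-serious. After the 6-month visit, the next scheduled laboratory tests are at the 9-month visit, 270 ± 30, that is days 240 to 300. After a day-150 visit, no protocol test falls on or before day 180.

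**3. Relatedness.** The rule is stated in 4.2 and absent from the other five places. Section 10 matters most, since it states the hypotheses and assigns the test.

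**4. Scale at 10 per arm.** One reclassified patient moves that arm's rate by 1/10 = 10 percentage points.
- Exact (Clopper-Pearson) 95% intervals: 0/10, 0 to 30.8%; 1/10, 0.3 to 44.5%; 2/10, 2.5 to 55.6%; 3/10, 6.7 to 65.2%.
- Two-sided Fisher p-values: 4/10 v 0/10, 0.087; 5/10 v 0/10, 0.033. No table with at most 4/10 in each arm goes below 0.087.

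The 0.05 level used to read these p-values is an assumption. The figures describe any binary endpoint at this sample size. They show what one patient is worth, not how often misclassification would occur.

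**The case against.** **On recording.** The shortfall exists only if 6 months is a fixed day. The schedule treats it as a visit, and on that reading nothing is lost. Even on the day-180 reading, a missed event would have to be non-serious and found outside the scheduled tests, for example on review of the medical record. The important-medical-event criterion in 13.1.2 names blood dyscrasias without hospitalization, so some grade 4 blood-count events would be serious and have the 30-day period. All of this stands and keeps the effect small. It does not remove the conflict between 13.3 and 13.4 over what is to be recorded.

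**On relatedness.** Section 4.2 is the objectives section, it states the rule clearly, and nothing contradicts it. *Any* may mean any type of toxicity. Table 1 justifies the endpoint by the harm each treatment may do to the surrounding liver, which fits treatment-related events. The protocol keeps the broad sense for adverse events, defined as "whether or not considered intervention related", and uses *toxicities* for treatment effects (2.3). Adverse events are recorded regardless of relationship and then attributed, so either numerator can be derived later. This also stands: the fault is an incomplete specification in section 10.

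**Stronger readings that the documents do not support.**
- A reader might infer two rival endpoints, related and all-cause. Omitting a rule is not reversing it.
- A reader might take 23 of 61 as the share of patients with lost data. It counts permitted visit days and is not a probability.
- A reader might treat 10.5.4 as a third recording period. It speaks of monitoring throughout the study, which can coexist with a recording cut-off, since 13.4 follows related events to resolution after the 6-month visit.
- A reader might think the unit is undecided. The synopsis, 4.2 and the 10.5.3 analysis line are per patient; the wording elsewhere is loose.
- The reference to section 12.4 is clerical; 13.4 holds the matching 30-day text.

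**Conclusion.** The conflict over the recording period is real and is wrong as written. For non-serious events the two rules differ by 30 − 7 = 23 days for every patient. Whether that reaches the endpoint depends on an assumption the plan leaves open. With the window closing on day 180, the 7-day rule falls short by 1 to 23 days for visits on days 150 to 172; with the window closing at the visit, it never does. The events at risk are few in kind: non-serious, grade 4 or higher, and found outside scheduled tests. The plan gives no rate from which to estimate how many.

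The relatedness omission is secondary. Section 4.2 governs, but the section that defines the test should say so.

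Severity is minor. The comparison is an unpowered secondary one in a 20-patient feasibility pilot. The primary objective and the sample size are unaffected.

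**What to change.** 1. Reconcile 13.3, 13.4 and footnote H to one recording period that covers the 6-month toxicity window even after a day-150 visit. State in 4.2 the day on which that window closes. The two must be settled together: a 30-day period covers a window closing on day 180 but can miss up to 3 days of one closing on day 183. Correct footnote H's cross-reference in the same edit.
2. In 10.2.2 and 10.5.3, state the endpoint as 4.2 has it: the proportion of patients with at least one CTCAE v5.0 grade 4 or higher event attributed as possible, probable or definite (Table 2), up to 6 months after treatment. Name this as the result tested by Fisher's exact test. If an all-cause endpoint is intended, amend 4.2 before analysis. The synopsis, Table 1 and 8.2 can be aligned at the same time.
3. Tabulate the all-cause per-patient proportion by arm beside the related one, with exact 95% confidence intervals. This does not remove the influence of unblinded attribution, but it shows how far the result depends on it.

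**Cost.** Wording changes, one extra table and, if 13.3 is aligned with 13.4, up to 23 more days of non-serious recording per patient, which 13.4 already requires. No new visits, patients or data items are needed.
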